**Protocol Synopsis:**

**Title of study:** Phase 2 study of decitabine and cedazuridine in combination with venetoclax for AML relapse after allogeneic hematopoietic cell transplantation

**Indication:** Post-transplant acute myeloid leukemia

**Study Phase:** II

**Objectives:**

Primary objective:

1. To assess the effect of DEC-C/venetoclax on the investigator-assessed composite CR rate (CR/CRh/CRi)

Secondary objectives:

1. To assess the rate of partial response (PR) and morphologic leukemia free state (MLFS) following treatment with DEC-C/venetoclax
2. To assess the relapse free survival of patients treated with DEC-C/venetoclax
3. To assess overall survival of patients treated with DEC-C/venetoclax
4. To assess the safety and tolerability of DEC-C/venetoclax in the post-HCT setting
5. To assess the rates of measurable residual disease negativity in patients achieving a CR.

**Background and Study Rationale:**

Acute myeloid leukemia, excluding acute promyelocytic leukemia, is generally associated with poor clinical outcomes. Patients with poor-risk clinical and molecular features experience a shortened survival with a minority surviving beyond 5 years. Similarly, patients with high-grade myeloid malignancies, including myelodysplastic syndrome (MDS) and chronic myelomonocytic leukemia (CMML), are at risk for leukemic transformation with rates approaching 40%. For poor-risk patients, allogeneic HCT is the only potentially curative therapy, however, post-HCT relapse is common and as many 85% of poor-risk AML patients will experience recurrence of their underlying disease. In a registry analysis, 15% of post-HCT relapsed AML patients achieved a subsequent complete remission (CR). Less than 5% of patients who relapsed within 6 months, and 12% of patients who relapsed 6-24 months after HCT were alive at 3 years.

Dysregulation of anti-apoptotic proteins, including BCL2, is responsible for tumor maintenance and survival. Venetoclax is a selective BCL2 inhibitor that increases cell death/apoptosis in hematologic malignancies. In chronic lymphoid leukemia, a disease heavily reliant on the loss of apoptosis, overall response rates (ORR) exceed 80% with venetoclax. In AML, anti-apoptotic pathways are more heterogeneous. Venetoclax, in combination with DNMTis or low dose cytarabine, results in CR/CRi rates of 60-75% in the treatment naïve (TN) setting. Off-label use in the relapsed/refractory (R/R)

disease is an emerging treatment paradigm with an ORR of 12-51%. In a series of post-HCT AML patients treated with venetoclax-based salvage therapies at Vanderbilt University Medical Center (16/21 with a DNMTi partner), we found the combination is safe and effective with an ORR of 42.1%. Interrupting therapy in patients with a treatment response was associated with improved safety and reduced toxicity after HCT.

Based on our published experience, and other retrospective data in R/R AML, we plan a phase 2 trial to prospectively assess the ORR of venetoclax/DNMTi salvage therapy after allogeneic HCT. Partnering venetoclax with DEC-C is an intuitive extension of our prior work and combines the efficacy of venetoclax/DNMTi therapy with the convenience of an all-oral treatment regimen which will improve quality of life compared to conventional salvage therapies.

### **Study Design:**

This is an open-label, non-randomized, investigator-sponsored, phase II study of venetoclax in combination with DEC-C in patients with myeloid diseases who relapse with AML after allogeneic HCT.

### **Patient Populations:**

Adult patients,  $\geq 18$  years of age with relapse/progression to AML after allogeneic HCT, who have not previously progressed while receiving venetoclax or other BCL-2 inhibitor, are eligible. Subjects with active GVHD, acute or uncontrolled infections, or with white blood cell count  $\geq 25,000/\mu\text{l}$  that cannot be controlled with hydroxyurea are not eligible.

Patients who develop grade 2-4 graft versus host disease while on study will have treatment interrupted. Subjects will be eligible to resume therapy after GVHD returns to  $\leq$  grade 1 after discussion with the study co-chair(s).

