## 4 STUDY POPULATION SELECTION

### 4.1 Study Population

Adult patients,  $\geq 18$  years of age with relapsed/progression to AML after allogeneic HCT, who have not previously progressed while receiving venetoclax or other BCL-2 inhibitor, are eligible. Subjects with active GVHD, acute or uncontrolled infections, or with white blood cell count  $\geq 25,000/\mu\text{l}$  that cannot be controlled with hydroxyurea are not eligible.

Patients who develop grade 3/4 graft versus host disease while on study will have treatment interrupted. Subjects will be eligible to resume therapy after GVHD returns to  $\leq$  grade 1 after discussion with the study co-chair(s).

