### 5.2.4 Dose-Limiting Toxicity

A dose-limiting toxicity (DLT) is defined as any toxicity that occurs up to day 28 during the dose de-escalation (pre-remission) phase and is at least possibly related to study drug administration. This does not include toxicity with a clear alternative explanation (e.g., disease progression) or transient ( $\leq 72$  hours) abnormal laboratory values without

associated clinically significant signs or symptoms based on investigator determination. All DLTs will be assessed by the investigator using CTCAE v5.0 criteria.

To be considered evaluable, subjects must fulfill the following minimum criteria:

- All doses of DEC-C.
- 75% of doses of venetoclax during the first cycle (e.g., 21/28 or 16/21 days)

All patients who initiate venetoclax/DEC-C, receive at least one dose of each, and experience a DLT are evaluable regardless of whether the minimum criteria above are met.

Subjects experiencing toxicity that results in dose-holds will remain evaluable provided the minimum criteria outlined above are met. Patients that require dose reductions during the DLT evaluation period (e.g., first 28 days after initiation of the first dose of study treatment/C1D1) will not be considered a DLT so long as they receive the minimum doses at the prescribed dose level outlined above.

Patients who achieve a morphologic remission on C1D22 BMBx, have not experienced a DLT, and have treatment interrupted due to favorable treatment response will be considered evaluable if they complete 75% of protocol-directed doses (i.e., a patient who achieves a remission and is instructed to stop venetoclax on C1D24 is considered evaluable provided they received at least 18/24 venetoclax doses, or 75%) and will not be replaced.

Patients missing >25% of venetoclax doses, or any DEC-C doses due to adverse event(s), will be considered a DLT provided the AEs are considered related. If unrelated, the patient may be replaced as described above.

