#### Pre-remission Phase

Treatment interruptions during the pre-remission phase, as well as the reason, must be documented.

Dose reductions are to be avoided for patients during cycle 1 in the dose finding portion of the study. [Figure 1](#) and [Table 5](#) summarizes the starting doses (Dose Level 1) and dose levels. General supportive care guidelines are provided in [Section 5.2.6](#). Outside of the dose finding portion of the study, dose reductions of venetoclax and/or DEC-C for adverse events may take place at any time as otherwise consistent with the protocol.

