#### **10.6.6 Auditing and Monitoring:**

The Vanderbilt-Ingram Cancer Center (VICC) oversees patient safety and data monitoring for its investigator-initiated and NIH-NCI funded clinical trials through its Data and Safety Monitoring Committee (DSMC). The purpose of the DSMC is to ensure the efficient implementation and management of the VICC Data and Safety Monitoring Plan (DSMP). The Committee maintains authority to intervene in the conduct of studies as necessary to ensure clinical research performed at VICC achieves the highest quality standards.

The VICC DSMC meets on a quarterly basis and ad hoc to discuss data and safety monitoring of clinical trials and to oversee the VICC DSMP. Internal audits for compliance with adverse event reporting, regulatory and study requirements, and data accuracy and completion are conducted according to the VICC DSMP according to study phase and risk. The committee reviews all serious adverse events (SAE) on Vanderbilt sponsored investigator-initiated studies on a quarterly basis and provides DSMC SAE review reports to the Vanderbilt IRB.

The trial additionally will be monitored by the VICC Multi-Institutional Coordinating Center. The actual frequency of monitoring will depend on the enrollment rate and performance of the site. Monitoring will be conducted through onsite and/or remote monitoring, teleconferences with the Investigator and site staff, and appropriate communications by mail, fax, email, or telephone. The purpose of monitoring is to ensure that the study is conducted in compliance with the protocol, standard operating procedures (SOPs), and other written instructions, and to ensure the quality and integrity of the data.

During scheduled monitoring visits, investigators and the investigational site staff must be available to discuss the progress of the trial, make necessary corrections to case report form entries, respond to data clarification requests, provide required regulatory documents, and respond to any other trial-related inquiries of the monitor.

In addition to the above, the FDA may review the conduct or results of the study at the investigational site.

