### **10.6.10 Protocol Deviations**

The Coordinating Center is responsible for implementing and maintaining quality assurance and quality control to ensure that studies are conducted according to the protocol, GCP, and all applicable regulatory requirements. A protocol deviation is any noncompliance with the protocol. Noncompliance can be on the part of the study participant, the investigator, or the study site staff. Deviations to the protocol are not permitted except when necessary to eliminate an immediate hazard to study subjects.

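### The Synopsis requires treatment to be held for grade 2-4 GVHD, Section 4.1 only for grade 3/4, and nothing says which governs

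*Combined protocol and SAP*

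**What the plan says.** The Synopsis, under Patient Populations, states: "Patients who develop grade 2-4 graft versus host disease while on study will have treatment interrupted". Section 4.1, Study Population, states: "Patients who develop grade 3/4 graft versus host disease while on study will have treatment interrupted".

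The resumption rule is the same in both places: "Subjects will be eligible to resume therapy after GVHD returns to" grade 1 or lower, once the case has been discussed with the study co-chair(s).

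The only other mention of GVHD is exclusion criterion 5 (Synopsis and Section 4.3), which governs entry and sets no on-study rule.

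**The concern.** An operative safety threshold is stated two ways. A site working from the Synopsis must stop both drugs at grade 2 GVHD; a site working from Section 4.1 may continue. The population is entirely post-transplant, and safety in that setting is a secondary objective, so this rule can be expected to matter in practice.

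Two things are at stake.

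- **Consistent conduct.** The same grade 2 event can be handled differently from site to site.
- **Compliance.** Section 10.6.10 says "A protocol deviation is any noncompliance with the protocol", and Section 10.6.6 says "The purpose of monitoring is to ensure that the study is conducted in compliance with the protocol". Dosing through grade 2 GVHD breaks the Synopsis and is consistent with Section 4.1.

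A secondary, conditional effect runs through the missed-dose rule in Section 5.2.4: "Patients missing >25% of venetoclax doses, or any DEC-C doses due to adverse event(s), will be considered a DLT", provided the events are considered related. A hold that one text makes mandatory and the other does not could therefore, in some patients, decide whether a DLT is counted.

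**Working it through.** No figure in the plan rests on this rule, so the main check is a comparison of text.

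**1. The two rules by grade**

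| New on-study GVHD | Synopsis | Section 4.1 |
|---|---|---|
| Grade 1 | no mandatory hold | no mandatory hold |
| Grade 2 | hold required | hold not required |
| Grade 3 or 4 | hold required | hold required |

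They differ only at grade 2.

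**2. Does any other text settle it?**

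- Section 5.2.4 (DLT definition and exceptions), Section 5.2.6 (supportive care and dose reduction), Table 7 and the non-hematologic delay list in Section 5.2.7 (creatinine, bilirubin, AST/ALT, infection), and Section 5.2.13 (off-treatment) do not name GVHD.
- Holds before remission are possible. Section 5.2.6.3 says "Treatment interruptions during the pre-remission phase, as well as the reason, must be documented", and Section 5.2.4 says "Subjects experiencing toxicity that results in dose-holds will remain evaluable provided the minimum criteria outlined above are met". After remission, Section 5.2.6.3 lets the investigator delay either drug for any adverse event. These provisions allow a grade 2 hold; none says whether it is mandatory.
- The text under Table 5 leans the other way before remission: venetoclax is meant to run continuously unless the day 22 marrow is clear of leukemia.
- The shared resumption level does not reveal which threshold was intended. Resuming at grade 1 or lower fits a grade 2 trigger, but it also fits a grade 3 trigger: Table 7 likewise stops at one grade (4) and resumes at a lower one (2 or below).

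**3. When a hold could count as a DLT**

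Inputs: the more-than-25% venetoclax rule and the any-DEC-C-dose rule (Section 5.2.4), the dose levels (Table 5) and the decision rules (Table 4).

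- *Dose levels 1 and -1, 28 scheduled venetoclax doses.* 7/28 = 25.0%, which does not exceed 25%; 8/28 = 28.6%, which does. Days 21 to 28 make 8 doses, so a hold lasting to the end of the cycle must start by day 21.
- *Dose level -2, 21 scheduled doses.* 5/21 = 23.8%, not exceeded; 6/21 = 28.6%, exceeded. Days 16 to 21 make 6 doses, so a hold lasting to the end of dosing must start by day 16.
- These agree with the plan's own minimums: 28 − 7 = 21 of 28, and 21 − 5 = 16 of 21.
- *Venetoclax stopped early for remission.* In Section 5.2.4's example of a stop on day 24, the minimum is 18/24. More than 25% of 24 is 7 doses (7/24 = 29.2%), and days 18 to 24 make 7, so a hold running to day 24 must start by day 18.
- *DEC-C route.* Onset must fall within dosing days 1-5 (level 1) or 1-4 (levels -1 and -2).

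Under Table 4, one such DLT could turn 1 of 6 (proceed as RP2D) into 2 of 6 (next lower dose level).

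The documents give no GVHD incidence, so no probability is attached to this chain. A site following Section 4.1 may also choose to hold, so only holds made solely because they are mandatory would differ.

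**The case against.** The strongest reply is that the two sentences impose no incompatible duties. Section 4.1 does not tell anyone to keep dosing at grade 2; it only leaves grade 2 out of the mandatory hold. Holding at grade 2 satisfies both texts. The Synopsis is also part of the protocol, so on a literal reading dosing through grade 2 is already noncompliance. This stands in part: a cautious site has a compliant course today, and a monitor who applies the Synopsis literally has an answer. It does not help a site that reads Section 4.1 as the full rule, and the text gives that site no reason to read it otherwise.

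Second, the DLT route is remote. It needs new grade 2 GVHD in the first 28 days, a hold made only because it is mandatory, a related event with no clear alternative explanation in patients who have all had an allogeneic transplant, enough missed doses, and no reclassification on review under the Section 5.2.4 exceptions. Entry also requires no active GVHD and at least 4 weeks off calcineurin inhibitors. All of this is fair, and the DLT route should carry no weight in judging severity. The day limits above also depend on the number of scheduled doses; Section 5.2.6.3 separately says that stopping for an aplastic, AML-negative marrow does not affect evaluability.

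Third, Figures 1 and 2, which Section 5.2.1 makes part of the dosing instructions, could not be read. The finding that nothing resolves the conflict therefore covers text and tables only.

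**Conclusion.** The inconsistency is real and should be corrected. Two mandatory safety sentences, both current, differ at one grade, and no readable text settles which applies. The consequence is unclear conduct and uneven deviation handling for new grade 2 GVHD.

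Its frequency cannot be sized from the documents. The effect on DLT counts is possible but conditional, and the primary efficacy test is not directly affected. Confidence in the discrepancy is high. It assumes that neither unread figure contains a GVHD rule. The documents do not show which threshold was intended.

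**What to change.** Choose one grade range and state it identically in the Synopsis (Patient Populations) and Section 4.1. Grade 2-4 is the more conservative option and complies with both current texts; it costs somewhat more dose interruption at grade 2. Grade 3/4 is workable if that was the intention, and leaves grade 2 holds to the investigator's judgement. The resumption rule suits either choice and need not change. Repeating the chosen rule in Section 5.2.7, where sites look for dose modifications, would also help.

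The minimum edit is the grade range in one sentence. It needs Coordinating Center review and IRB approval at each institution (Sections 10.1, 10.6.1 and 10.6.11).

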### **Inclusion Criteria:**

1. Age  $\geq 18$  years at the time of signing the Informed Consent Form (ICF); must voluntarily sign an ICF and meet all study requirements
2. History of morphologically confirmed AML (per WHO diagnostic criteria) with evidence of disease recurrence ( $\geq 5\%$  blasts consistent with prior disease) that occurs after allogeneic HCT. Patients transplanted for another indication (e.g., MDS/CMMI) who relapse with AML are eligible to enroll.
3. WBC must be less than  $25,000/\mu\text{l}$  for at least three days prior to C1D1 (hydroxyurea allowed).
4. A bone marrow biopsy must be performed and tissue collected for entrance to the trial
5. Eastern Cooperative Oncology Group Performance Status of 0 - 2
6. Must have adequate hepatic and renal function as demonstrated by the following: ALT (SGPT) and/or AST (SGOT) less than or equal to 3x upper limit of normal (ULN); total bilirubin  $< 1.5 \times$  upper limit of normal (ULN). Patients with Gilbert's syndrome (hereditary indirect hyperbilirubinemia) must have a total bilirubin of  $< 3 \times$

ULN; and calculated creatinine clearance  $\geq 30$  ml/min (per the Cockroft-Gault formula).

7. Willingness to abide by all study requirements, including contraception, maintenance of a pill diary, and acceptance of recommended supportive care medications.

**Exclusion Criteria:**

1. Prior relapse or progression while receiving venetoclax or other commercially available or investigational BCL-2 inhibitor.
2. Anticancer therapy, including investigational agents  $\leq 2$  weeks or  $\leq 5$  half-lives of the drug, whichever is shorter, prior to C1D1. (Use of hydroxyurea is permitted).
3. Inadequate recovery from toxicity attributed to prior anti-cancer therapy to  $\leq$ Grade 1 (NCI CTCAE v5.0), excluding alopecia or fatigue.
4. History of allogeneic hematopoietic cell transplantation (HCT), or other cellular therapy product, within 3 months of signing consent.
5. Clinically active acute or chronic GVHD. Patients must be off calcineurin inhibitors for at least 4 weeks to be eligible.
6. Radiation therapy or major surgery within 3 weeks of signing consent.
7. Active, uncontrolled infection. Patients with infection under active treatment and controlled with antibiotics are eligible. Prophylaxis is acceptable.
8. Inability to tolerate oral medication, presence of poorly controlled gastrointestinal disease, or dysfunction that could affect study drug absorption.
9. Active documented central nervous system leukemia
10. Concurrent treatment with a non-permitted concomitant medication.
11. Other malignancy IF currently being treated or likely to be treated in next 6 months except for basal or squamous cell carcinoma of the skin or cervical carcinoma in situ.
12. Pregnancy or breastfeeding females
13. Known chronic alcohol or drug abuse
14. Clinically significant cardiovascular disease with major event or cardiac intervention within the past 6 months (e.g. percutaneous intervention, coronary artery bypass graft, documented cardiac heart failure) as determined by the investigator
15. Any other condition deemed by the investigator to make the patient a poor candidate for clinical trial and/or treatment with investigational agents.

**Dosing Rationale:**

At dose level one, subjects will receive escalating doses of venetoclax during a “ramp” phase to a maximum dose of 400mg/day, and then continuously thereafter. This dose was chosen based on the clinical trial dosing in combination with a DNMTi partner.

DEC-C will be dosed at decitabine 35mg and cedazuridine 100mg per day on days 1-5 which is consistent with prior study data and approval. Cycles are every 28 days.

**Study Duration:**

It is estimated that this study will enroll patients from January 2022 through January 2024. Data lock and study closure is expected in January 2025.

**Statistical Analysis:**

Assuming a historical ORR of 15%, per the phase II efficacy trial, Simon's optimal two-stage design calls for a total of 34 patients. A preliminary efficacy assessment will be performed following enrollment of the first 20 patients. If  $\geq 3/20$  enrolled patients achieve a CR, this is sufficient to continue enrollment for the remainder of the study. If  $\geq 9/34$  patients respond, we will reject ( $p < 0.05$ ) the null hypothesis that the true response rate of the regimen is less than or equal to 15%. If the true response rate is 35% or greater, this study design has 80% probability of rejecting the null hypothesis. If the true response rate is low at 15%, the probability of early termination is 60% with an expected sample size of 19 patients.

Toxicity will be monitored in the expansion phase using a Bayesian approach. Toxicity monitoring will begin when the 6th patient is evaluable for toxicity. It is expected that the toxicity rate is maintained at approximately 20% (maximum probability of DLT of 0.2, prior distribution (1,1), cohort size 1, and posterior probability  $> 80\%$ ). Enrollment will be paused if toxicity exceeds this rate.

The maximum number of patients enrolled (n=51) reflects an anticipated drop out of 15% (n=5) and enrollment of 6-12 additional patients if dose level 0 is deemed toxic.

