## **2 STUDY OBJECTIVES**

### **2.1 Primary Objectives:**

1. To assess the effect of DEC-C/venetoclax on the investigator-assessed composite CR rate (CR/CRh/CRi)

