### **2.2 Secondary Objectives:**

1. To assess the rate of partial response (PR) and morphologic leukemia free state (MLFS) following treatment with DEC-C/venetoclax
2. To assess the relapse free survival of patients treated with DEC-C/venetoclax
3. To assess overall survival of patients treated with DEC-C/venetoclax
4. To assess the safety and tolerability of DEC-C/venetoclax in the post-HCT setting
5. To assess the rates of measurable residual disease negativity in patients achieving a CR.

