### **9.2 Disease Assessments**

For the purposes of this analysis, responses will be assessed in accordance with the International Working Group (IWG) response criteria in acute myeloid leukemia.

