### **9.3 Dose De-escalation Design**

Assuming a historical ORR of 15%, per the phase II efficacy trial, Simon's optimal two-stage design calls for a total of 34 patients. A preliminary efficacy assessment will be performed following enrollment of the first 20 patients. If  $\geq 3/20$  enrolled patients achieve a CR, this is sufficient to continue enrollment for the remainder of the study.

If  $>9/34$  patients respond, we will reject ( $p<0.05$ ) the null hypothesis that the true response rate of the regimen is less than or equal to 15%. If the true response rate is 35% or greater, this study design has 80% probability of rejecting the null hypothesis. If the true response rate is low at 15%, the probability of early termination is 60% with an expected sample size of 19 patients.

The maximum number of patients enrolled ( $n=51$ ) reflects an anticipated drop out of 15% ( $n=5$ ) and enrollment of 6-12 additional patients if dose level 0 is deemed toxic.

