### 9.3.1 General Analysis Considerations

Continuous variables (e.g., age) will be summarized using the minimum, 25th, 50th (median), 75th, and maximum values along with the mean and standard deviation, as appropriate. Generally, rank based nonparametric tests will be used to compare continuous variables among patient subgroups. Categorical variables (e.g., objective response) will be summarized in frequency tables and compared among patient subgroups using the chi-square test. Linear regression and logistic (or ordinal logistic) regression will be used to construct multivariable models for continuous, binary, and ordinal variables, as appropriate. In addition to ORR, the distributions of progression-free and overall survival will be estimated using the Kaplan-Meier method. We will consider statistical comparisons statistically, but not necessarily clinically, significant for  $p<0.05$ .

Dose limiting toxicity (see [Section 5.2.4](#)) will be monitored in this phase II clinical trial using a Bayesian approach. A maximum of 34 patients will be enrolled and toxicity monitoring will begin when the 6th patient is evaluable for toxicity. It is expected that the toxicity rate is maintained at approximately 20% (maximum probability of DLT of 0.2, prior distribution (1,1), cohort size 1, and posterior probability  $> 80\%$ ). Pursuant to this rule, patients will be monitored according to the stopping boundaries outlined in [Table 10](#). For example, the protocol will pause for review due to excessive toxicity if 2 or more DLTs are experienced by the first 6 patients treated. 9 DLTs will be allowed among 34 patients treated.

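### The interim and final decision rules are not tied to the sole primary endpoint, composite CR (CR/CRh/CRi)

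*Combined protocol and SAP*

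**What the plan says.** Section 2.1 (and the synopsis objectives) gives one primary objective: "To assess the effect of DEC-C/venetoclax on the investigator-assessed composite CR rate (CR/CRh/CRi"). Section 2.2 makes PR and MLFS a separate secondary objective: "To assess the rate of partial response (PR) and morphologic leukemia free state (MLFS) following treatment with DEC-C/venetoclax".

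The decision rules stand in the synopsis, under Statistical Analysis, and again in Section 9.3. They use three other terms:

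- **Null.** The design starts from an ORR: "Assuming a historical ORR of 15%, per the phase II efficacy trial". The hypothesis is then worded as "the null hypothesis that the true response rate of the regimen is less than or equal to 15" percent.
- **Interim.** If at least 3 of 20 "enrolled patients achieve a CR, this is sufficient to continue enrollment for the remainder of the study".
- **Final.** The count is of patients who respond, at least 9 of 34 in the synopsis and more than 9 of 34 in Section 9.3.

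The other analysis sections do not supply the link. Section 9.2 says "responses will be assessed in accordance with the International Working Group (IWG) response criteria in acute myeloid leukemia", without saying which categories are successes. Section 9.3.1 writes "Categorical variables (e.g., objective response) will be summarized in frequency tables" and "In addition to ORR, the distributions of progression-free and overall survival will be estimated using the Kaplan-Meier method". The abbreviation ORR is expanded in the background only as overall response rate, with no categories listed.

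**The concern.** A two-stage design has one counted event, and its operating characteristics belong to that event. Here the reader has to infer it. Taken at their word, the rules count strict CR at the interim, which leaves out CRh and CRi, and count response at the end, which can take in PR and MLFS.

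A different interim event is not invalid in itself, but it has to be named and the operating characteristics worked out for it. The plan gives p<0.05, 80% power, 60% early termination and 19 expected patients for a single response rate.

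This is the trial's only efficacy go/no-go. Two analysts with the same data could reach different decisions. Because the study is open-label and investigator-assessed, the choice of event could be made after responses are known.

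**Working it through.** **Inputs from the plan.** Null 15%, alternative 35%, N = 34; interim at 20 patients with at least 3 needed; final cut-off at least 9 (synopsis) or more than 9, that is at least 10 (Section 9.3). The two final cut-offs conflict, so both are run. **Assumed:** every split between strict CR, composite CR and PR/MLFS, since the documents give none.

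**Step 1: reproduce the plan's figures.** An exact search for the Simon optimal design (15% against 35%, one-sided alpha at most 0.05, power at least 0.80) gives: continue with at least 2/9, reject with at least 9/34.

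- Early termination at 15%: P(X ≤ 1 | 9, 0.15) = 0.85^9 + 9 × 0.15 × 0.85^8 = 0.5995.
- Expected N: 9 + (1 − 0.5995) × 25 = 19.0.
- Alpha 0.047, power 0.811.

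So the stated 34, 80%, 60% and 19 come from one event with one rate under each hypothesis. The written 3/20 interim gives early termination 0.405 and expected N = 20 + 0.595 × 14 = 28.3. That mismatch is a separate issue.

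**Step 2: strict CR at the interim, composite at the end, true composite CR 35%.** Let s be the strict CR rate and q the rate of the final event, which includes strict CR.

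- Stop = P(X ≤ 2 | 20, s). At s = 0.15: 0.0388 + 0.1368 + 0.2293 = 0.4049.
- Success = sum over x ≥ 3 strict CRs and y other final-event patients among the first 20 of [trinomial probability of (x, y)] × P(Bin(14, q) ≥ c − x − y), with c = 9 or 10.

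| Strict CR rate | Stop at 20 | Success, at least 9/34 | Success, more than 9/34 |
|---|---|---|---|
| 35% (composite counted) | 1.2% | 0.889 | 0.804 |
| 28% (80% of composite) | 5.3% | 0.867 | 0.788 |
| 25% | 9.1% | 0.838 | 0.767 |
| 20% | 20.6% | 0.744 | 0.689 |
| 15% | 40.5% | 0.566 | 0.531 |

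**Step 3: strict CR at the interim, PR/MLFS added at the end, true composite CR 15%.** Same formula, with q = 0.17 (2 points added) or 0.20 (5 points added).

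| Strict CR rate | +2, at least 9/34 | +2, more than 9/34 | +5, at least 9/34 | +5, more than 9/34 |
|---|---|---|---|---|
| 7.5% | 0.054 | 0.029 | 0.087 | 0.055 |
| 10% | 0.080 | 0.040 | 0.137 | 0.084 |
| 15% | 0.107 | 0.051 | 0.204 | 0.117 |
| Composite at both looks | 0.058 | 0.024 | 0.058 | 0.024 |

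The low ends occur when strict CR is low, because a strict interim partly offsets a lenient final count.

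**Step 4: does the direction depend on the 3/20 rule?** Under the 2/9 interim that matches the stated figures:

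- Composite CR 35%, strict CR 25/20/15%: stopping is 30.0/43.6/60.0% against 12.1%; success with at least 9/34 is 0.655/0.531/0.380 against 0.811.
- Composite CR 15%, 5 points added: false success is 6 to 15% against 4.7% (at least 9/34), or 4 to 9% against 2.1% (more than 9/34).
- Composite CR 15%, 2 points added: 4 to 8%, or 2 to 4%.

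The direction is the same.

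**The case against.** The strongest reply is that these are loose words for one event. The text describes a single Simon design with one null, one alternative and one true response rate, and its figures reproduce on that basis. Composite CR is the sole primary objective, with its categories listed. PR and MLFS are set apart as secondary. Section 5.2.6.2 speaks of patients who have a CR together with prolonged neutropenia, which suggests that CR is sometimes used loosely. A narrow interim event paired with a wider final one is the least natural reading. The objective-response wording in Section 9.3.1 is only an example of a categorical variable and proves little.

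Much of this stands. A reader might infer that the response categories are listed nowhere; they are listed in the objectives, and only the link to the rules is missing. A reader might also infer that the trial is set to test the wrong endpoint; the documents do not support that, because the shorthand reading remains open.

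It does not settle the matter. The protocol elsewhere reports CR/CRi rates and ORR as separate measures, and Section 1.1 says the trial will assess ORR. So a single-event reading could equally be ORR. In that case, PR/MLFS adding 5 points at both looks to a composite CR of 15% gives success probabilities of 0.225 (at least 9/34) or 0.125 (more than 9/34).

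The objection on size also stands. The largest losses need fewer than half of composite responders to be strict CRs; at 80%, stopping is 5.3% and success 0.867 against 0.889. The 20% false-success figure assumes that all composite responders are strict CRs.

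**Conclusion.** The point holds as a missing link: neither decision rule, nor the null, is tied to composite CR, and following the words literally tests a different event from the primary endpoint. The wording defect is certain; its effect on decisions is not.

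The figures in the working show what could happen under assumed splits. A reader might take 40.5% stopping or 20% false success as the trial's actual error rates. The documents do not support that: they give no split, and if every term means composite CR there is no effect at all. With PR/MLFS adding 2 points the effect is small: 5 to 11% against 5.8%, or 3 to 5% against 2.4%.

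Nor do the documents show that 15% is a composite-CR rate. The only other 15% response figure, in the synopsis background and Section 1.1, is a registry rate of complete remission.

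The mismatch of 3/20 with the stated 60% and 19 patients, and the conflict between the two final cut-offs, are separate issues and add no weight here.

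**What to change.** Before any interim or final count is made:

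- In the synopsis and Section 9.3, name composite CR (CR/CRh/CRi) as the counted event in the null, the alternative, the interim rule and the final rule.
- State that PR and MLFS count toward neither cut-off.
- Give the source of the 15% and justify it as a null for composite CR. If it cannot be justified for that endpoint, restate the null and the operating characteristics.
- Report strict CR and ORR descriptively, with the categories in ORR listed.

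The cost is wording in two places, one source statement and two descriptive tabulations. If 15% can be justified for composite CR, this fix leaves N = 34 and the cut-offs alone; if it cannot, the design has to be re-derived. The downside for the sponsor is that the headline rate may be lower than an ORR.
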